#### 14.3.1.6. Secondary Estimand (Hypothetical)

The secondary estimand for the primary endpoint is defined as follows:

- Treatment difference in ICP measurement between Presendin and placebo at Week 24 for all patients who are randomised and start treatment, if all patients adhered to treatment, where patients did not have medications or procedures likely to materially affect ICP.

The secondary estimand for the initial secondary endpoint will be defined as:

- Treatment difference in PMD between Presendin and placebo over 24-weeks for all patients who are randomised and start treatment, if all patients adhered to treatment, where patients did not have medications or procedures likely to materially affect PMD.

All details will be defined in the SAP.

#### 14.3.2. Analysis Populations

The following analysis populations are planned for this trial:

- **Safety Population:** The Safety population includes all patients randomised to treatment who receive at least one dose of trial medication. This will be the population used for all safety analyses unless otherwise specified.
- **Intent-To-Treat Population (ITT):** The ITT population includes all patients randomised to treatment. This will be the main population for all efficacy analyses unless otherwise specified.
- **Per Protocol (PP):** The PP population includes all patients randomised to treatment without important non-evaluable protocol deviations. Only protocol deviations with the potential to affect the trial results significantly, or to invalidate the interpretation of the data obtained, will lead to exclusion of patients from the PP population. Protocol deviations to be considered will include (but will not be limited to):
  - Failure to meet inclusion/exclusion criteria
  - Wrong treatment or incorrect volume of drug administration
  - Prohibited concomitant medications
  - Compliance of less than 75% or >125% with trial drug administration

Study Number: INVEX-CLIN-IIH-301 Protocol	Compound No.: Presendin
	Version: 5.0 for EU countries dated 08Dec2022

- Use of rescue procedures, including, off-protocol LPs, LP shunts or bariatric surgery

Assignment of patients to populations will be confirmed at a blinded data review meeting to be held before the trial database is locked.

If a patient is randomised incorrectly or is administered the incorrect trial medication, analyses of the ITT will be based on the assigned treatment, whereas all other analyses will be based on the actual treatment received.

### 14.3.3. Treatment Comparisons

Treatment comparisons will be undertaken between active and control groups. The primary outcome will be analysed as described in Section 13.2.1.

### 14.3.4. Safety Analyses

Safety will be evaluated from reported AEs, changes in clinical laboratory values, changes in vital signs, and ECG results.

All safety analyses will be performed on the Safety population.

#### 14.3.4.1. Adverse Events

All AEs, TEAEs, and SAEs will be coded using the MedDRA dictionary (the most recent version before starting the trial will be used).

An AE is defined as treatment-emergent if the first onset or worsening is after the first administration of trial medication.

The number and percentage of patients reporting TEAEs, grouped by MedDRA system organ class and preferred term will be tabulated by treatment group. Summaries will be presented for all TEAEs, TEAEs by severity and TEAEs by relationship to trial medication.

In the AE data listings, all AEs will be displayed. Adverse events that are not treatment-emergent will be flagged. The observation period in which an AE started will also be provided.

Non-protocol LPs, interventions for IIH, hospital admission for IIH exacerbation will be displayed by trial arm. Treatment failures will be displayed by trial arm.

Study Number: INVEX-CLIN-IIH-301 Protocol	Compound No.: Presendin
	Version: 5.0 for EU countries dated 08Dec2022

#### **14.3.4.2. Clinical Laboratory Evaluations**

Laboratory test results for each biochemistry and haematology parameter will be summarized descriptively by treatment group and time point as both observed values and change from baseline values.

The number of patients with clinical laboratory (biochemistry, haematology, and urinalysis) values categorized as below, within, or above the normal ranges (or as either normal or abnormal for urinalysis variables that do not have quantitative ranges), will be tabulated in relation to baseline (shift tables), for each clinical laboratory analyte by treatment group and time point.

Laboratory values will be displayed in the data listings and those that are outside the reference ranges will be flagged, along with corresponding normal ranges. Any patients with any markedly abnormal laboratory results will also be provided in a listing.

Pregnancy test results including reason, if not performed, will be listed.

#### **14.3.4.3. Vital Signs and Body Mass Index Evaluations**

Descriptive summaries of observed values and changes from baseline will be calculated for systolic blood pressure, diastolic blood pressure and heart rate by treatment group and time point.

Body mass index will be derived at Screening, Baseline and Weeks 4, 8, 16, 24, 32 and 48 using height captured at Screening and weight at the respective assessment. Body mass index and weight will be summarized descriptively by treatment group and time point as both observed values and change from baseline values for Safety and ITT populations.

#### **14.3.4.4. Electrocardiogram**

Descriptive statistics of observed values and change from baseline will be presented for ECG measures of PR interval, QRS interval, QT interval, QT interval corrected according to Fridericia's formula (QTcF). These summaries will be presented by treatment and time point for the Safety population.

The number and percentage of patients with values beyond clinically important limits will be summarised including those with an increase in QTcF >30 msec increase from baseline and >60 msec increase from baseline or those with an absolute QTcF value of >450 msec (male patients) or >470 msec (female patients).

Study Number: INVEX-CLIN-IIH-301 Protocol	Compound No.: Presendin
	Version: 5.0 for EU countries dated 08Dec2022

#### 14.3.4.1. Other Safety Evaluations

Non-protocol LPs, interventions for IIH, hospital admission for IIH exacerbation will be displayed by trial arm.

#### 14.3.5. Patient Reported Outcomes Analyses

All patient reported outcome endpoints (VFQ-25, HIT-6, SF-36, EQ-5D-5L) will be analysed as observed and presented with change from baseline in a descriptive summary of treatment and visit

The number and percentages of PGIC responses will be tabulated by treatment and visit.

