### Quality of life in IIH

IIH has a detrimental effect on all aspects of the patient's quality of life; the majority of which is driven by headache [Kleinschmidt, 2000, Mulla, 2015; Daniels, 2007; Digre 2015]. IIH also impacts visual function with PMD correlating with quality of life [Bruce 2016]. Patient reported outcomes in clinical trials are essential not only to permit health technology assessments and cost effectiveness analysis, but also as key outcomes for a therapy's effectiveness [Deiner, 2019]. There is currently no IIH disease specific quality of life outcome measure.

Whilst there are differences in the choice of the tools used in the trials, they all commonly used the short-form 36 health survey (SF-36) [Mollan, 2021, Wall, 2014, Digre, 2015; Bruce, 2016; Ball, 2011]. The physical component score of the SF-36 has been shown to correlate significantly with changes in ICP [Grech 2021]. The EuroQol –5 dimension (EQ-5D-5L) [Euroqol, 1990] is typically employed for health technology assessments and cost effectiveness [Ottridge, 2017; Ball, 2011]. Using the EQ-5D-5L in isolation may lack sensitivity as compared to the SF-36 for IIH. The National Eye Institute Visual Function Questionnaire-25 and 10-item supplement [Mangione, 2001]

Study Number: INVEX-CLIN-IIH-301 Protocol	Compound No.: Presendin
	Version: 5.0 for EU countries dated 08Dec2022

has also been utilised to assess visual related quality of life in IIH and is associated with improvement in visual field [Bruce 2016; Mangione 1998; Raphael 2006]. The 10-Item neuro-ophthalmic supplement was found to be significantly discriminating in a previous IIH drug trial [Wall 2014].

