### **2.4. Exploratory Objectives**

To determine the effect of Presendin on:

- Macular ganglion cell layer/complex thickness
- Headache responder rate:  $\geq 30\%$  reduction in monthly headache days
- Headache responder rate:  $\geq 30\%$  reduction in moderate to severe monthly headache days
- Patient Reported Outcomes
- Body Mass Index
- Body Weight
- Health Utilisation

Study Number: INVEX-CLIN-IIH-301 Protocol	Compound No.: Presdin
	Version: 5.0 for EU countries dated 08Dec2022

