### 3.4. Exploratory Endpoints

- Macular ganglion cell layer/complex thickness
- Responder rate monthly headache days (defined as  $\geq 30\%$ )
- Responder rate moderate to severe monthly headache days (defined as  $\geq 30\%$  reduction)
- Patient Reported Outcomes (PRO):
  - Visual Function Questionnaire-25 and 10-item supplement
  - Headache Impact Test-6
  - 36-item short form survey
  - EuroQol -5 dimension -5 level survey
  - Patient Global Impression of Change
- Body Mass Index
- Body Weight
- Health Utilisation

Study Number: INVEX-CLIN-IIH-301 Protocol	Compound No.: Presendin
	Version: 5.0 for EU countries dated 08Dec2022

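### The exploratory objectives promise an effect of Presendin on patient-reported outcomes, body weight and BMI, but only descriptive summaries by arm are planned, with no between-arm estimate or confidence interval

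*Protocol*

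**What the plan says.** - **Objective.** Protocol section 2.4 opens its exploratory list with "To determine the effect of Presendin on"; PROs, BMI and body weight are on it.
- **Endpoints.** Section 3.4 places the same items in the exploratory tier. The vision instrument is a single entry: "Visual Function Questionnaire-25 and 10-item supplement".
- **PRO analysis.** Section 14.3.5 says that all PRO endpoints (VFQ-25, HIT-6, SF-36 and EQ-5D-5L in its parenthesis) "will be analysed as observed and presented with change from baseline in a descriptive summary of treatment and visit". For the global impression item, "The number and percentages of PGIC responses will be tabulated by treatment and visit".
- **Weight and BMI.** Section 14.3.4.3, under Safety Analyses: "Body mass index and weight will be summarized descriptively by treatment group and time point", as observed values and change from baseline.
- **Comparisons in general.** Section 14.3.3: "Treatment comparisons will be undertaken between active and control groups". The only method it then points to is the one for the primary outcome.
- **Role of the SAP.** Section 14 leaves to the SAP the detailed methods for the analyses that the protocol outlines.

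The version 4.0 text in the same file (sections 13.3.4.3 and 13.3.5) has the same wording on both points.

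**The concern.** An objective to determine an effect in a randomised, placebo-controlled trial calls for a comparison between arms with its uncertainty. Summaries of each arm's mean and change do not supply one. Change from baseline within an arm mixes any drug effect with the natural course of the disease and placebo response. Section 4.1.1 expects a placebo response in headache outcomes, which bears directly on HIT-6. As-observed means at successive visits may also cover different sets of patients.

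The stake is interpretive. Section 14.2.3.1 treats a 0.71 dB difference in perimetric mean deviation as clinically meaningful partly because general and visual quality of life also changed significantly in the earlier acetazolamide trial. This trial collects the same kind of data at baseline and six later clinic visits (Table 1, Visits 5 to 10), but plans no between-arm estimate that could give similar support to its own result.

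**Working it through.** **Step 1: is a comparison planned anywhere?** The protocol states no effect size, SD, power or sample size for PROs, weight or BMI, so there is no figure to reproduce. The check is of the text.

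| Place | What it covers | Between-arm estimate for PROs, weight or BMI? |
|---|---|---|
| 14.3.5 | PRO scores; global impression | No: descriptive by arm and visit; counts and percentages |
| 14.3.4.3 | Weight, BMI | No: descriptive by arm and time point |
| 14.3.3 | Comparisons in general | Names no PRO, model or estimate; refers to a method for the primary outcome only |
| 14.2.1.1 | ICP power | Baseline-adjusted ANCOVA, for ICP |
| 14.3.6 | Missing data | Describes imputation for primary and secondary efficacy endpoints |
| 14 (opening) | Scope of the SAP | Detail for analyses outlined; the one outlined for PROs is descriptive |

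No row supplies an effect estimate for the objectives in 2.4.

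**Step 2: illustration of what baseline adjustment would add.** This is not a loss in any planned analysis, because no formal comparison of change is planned.

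Inputs: 120 patients per arm (section 14.2.1), taken as complete; equal SD at baseline and follow-up (assumed); correlation r between baseline and follow-up of 0.3 to 0.7 (assumed, because the documents give none for these scores).

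Variance of the between-arm difference, in SD² units, with n per arm:

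- unadjusted change: 2 × 2(1 − r)/n
- baseline-adjusted: 2 × (1 − r²)/n
- ratio, unadjusted to adjusted: 2(1 − r)/(1 − r²) = 2/(1 + r)

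| r | SE, unadjusted change | SE, baseline-adjusted | Variance ratio |
|---|---|---|---|
| 0.3 | √(2.80/120) = 0.153 | √(1.82/120) = 0.123 | 2/1.3 = 1.54 |
| 0.5 | √(2.00/120) = 0.129 | √(1.50/120) = 0.112 | 2/1.5 = 1.33 |
| 0.7 | √(1.20/120) = 0.100 | √(1.02/120) = 0.092 | 2/1.7 = 1.18 |

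The unadjusted comparison therefore has 54%, 33% and 18% more variance. An assumed chance baseline imbalance of 0.2 SD would also move the raw-change difference by 0.2(1 − r) = 0.14, 0.10 and 0.06 SD relative to the adjusted one.

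**The case against.** The best reply is that these endpoints are exploratory. Descriptive reporting is common in that tier, and nothing primary or secondary depends on it. Section 14.3.3 speaks of treatment comparisons without limiting them to a tier, and an SAP that is not shown could add a model. Weight and BMI are summarised in a safety section, where descriptive tables are usual, and section 1.1 says separately that the impact of weight change on the outcomes will be evaluated. On this view the mismatch lies in one verb of the objective.

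The tier argument stands and limits the weight of the point. The rest does not close the gap. Section 14.3.3 is generic, while 14.3.5 is specific and descriptive. The SAP's stated task is to detail what is outlined. Evaluating how weight change bears on outcomes is a different question from the effect of Presendin on weight.

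Four stronger readings are tempting, but the documents do not support them:

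- **That the trial could say nothing about an effect on PROs.** The tables are by arm, so a crude unadjusted difference can be read from them. What is missing is a planned estimate with its uncertainty.
- **That the protocol ranks PROs as key outcomes of this trial.** The background section on quality of life describes PROs in clinical trials generally as essential, "but also as key outcomes for a therapy's effectiveness". Section 3.4 sets their rank here, and it is exploratory.
- **That the 10-item supplement is left unanalysed.** Section 14.3.5 covers all PRO endpoints, and 3.4 defines the questionnaire and supplement as one endpoint, so VFQ-25 is plausibly shorthand for both. This is a labelling clarification.
- **That keeping PRO values after rescue therapy or an off-protocol lumbar puncture is an error.** Keeping observed values is a legitimate choice. The rules in 14.3.1 are written for ICP, perimetric mean deviation, OCT and headache days, and they differ from one another, so they cannot simply be carried over.

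**Conclusion.** The point holds as a minor mismatch between objective and analysis. The protocol sets out to determine an effect on PROs, body weight and BMI, and fixes only as-observed summaries by arm and visit for them. Followed as written, it yields no between-arm estimate and no confidence interval for those exploratory objectives. Primary and secondary conclusions are untouched.

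This conclusion rests on the text alone. The 18% to 54% range only illustrates why a baseline-adjusted estimate is preferable to an unadjusted comparison of change. It depends on assumed correlations, equal variances and complete data, and should not be cited as efficiency that the trial loses. Adding the estimate is a cheap improvement, not a condition for the trial's validity.

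**What to change.** Keep the descriptive tables, including the tabulation of the global impression item. Add to section 14.3.5, with a cross-reference from 14.3.4.3:

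> Each continuous PRO score (VFQ-25 with the 10-item supplement, HIT-6, SF-36, EQ-5D-5L), and body weight and BMI, will be analysed by a mixed model for repeated measures on all scheduled post-baseline visits, with baseline value, the stratification factors, arm, visit and arm-by-visit interaction. The Week 24 difference between arms will be reported with a nominal 95% CI and labelled exploratory.

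Two clarifications go with it. Name the supplement in the list of instruments. Take the visits from Table 1, because 14.3.4.3 lists Weeks 32 and 48 for BMI, which Table 1 does not contain. The scores used for each instrument can be named in the SAP.

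The cost is a few standard model runs on data already collected. The downside is more nominal estimates without multiplicity control, which must be labelled so that none is read as confirmatory. If the sponsor prefers to stay descriptive, the minimum is to reword the objective in 2.4 for these items from determining an effect to describing the outcomes by arm.

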#### 14.3.6. Missing Data

Although every effort will be made to collect responses from all patients at all scheduled time points, there undoubtedly will be some missing data. The SAP describes in detail steps for dealing with missing data using relevant imputation strategies for specific endpoints that adjust for treatment arm, centre, baseline value, and stratification variables.

We briefly describe our imputation strategy for the analysis of primary and secondary efficacy endpoints here. Our imputation strategy generally applies for data being set to missing by having an intercurrent event or data that is not captured at all.

For the primary efficacy variable (lumbar puncture) there is only one post-baseline assessment planned at Week 24. In this case we will multiply impute missing values from the posterior predictive distribution of a generative regression model that will use explanatory variables:

- the randomisation stratification variables;
- treatment allocation;
- the baseline values of the outcome

Values for these variables must be established for all patients at baseline so we do not expect missing values here.

For outcomes with repeated measures (secondary efficacy variables), to the above list we will also add historic observations of the outcome in question, including imputed values. In chained equation models that seek to incrementally estimate repeated measures outwards from baseline, missing values are imputed for the first assessment time, then

Study Number: INVEX-CLIN-IIH-301 Protocol	Compound No.: Presendin
	Version: 5.0 for EU countries dated 08Dec2022

values for the first assessment are included when imputing missing values for the second assessment time, etc.

The above multiple imputation models for both primary and secondary efficacy endpoints will be applied in a way that missing data will be imputed in different ways dependent on the reason for missingness. In case the data can be assumed to be missing at random (e.g. early discontinuation from study due to withdrawal of consent), the missing data will be imputed using the treatment arm to which the patient was randomised to. In case the data needs to be assumed to be missing not at random (e.g. early discontinuation due to adverse event), the missing data will be imputed to reflect outcomes in the placebo arm (e.g. for endpoints that are observed once, like ICP), or to reflect changes through time that are typical in the placebo arm (e.g. for repeated measures endpoints, like headache days). A detailed list of reasons for missingness and the corresponding way of imputation will be specified in the SAP. For the analysis of the secondary estimands, the same model will be used, but additional treatment events will be considered which require further imputations.

In both cases, the imputation process will finally be repeated several times to reflect the uncertainty in missing values. The analysis method described in this protocol will be performed on each complete imputed dataset. Final estimates of the treatment effect and its uncertainty will be derived by combining the analyses on the complete imputed datasets using standard methods, described in several sources including. (White et al, 2011).

For the analysis of the primary efficacy endpoint and for some of the important secondary endpoints, further sensitivity analyses for missing values will be planned to investigate the effect of missing values on the results, using simpler statistical models. For the primary efficacy endpoint this will include a completer analysis, as well as an analysis using baseline observation carried forward (BOCF), for the important secondary endpoints this will cover a mixed model for repeated measures (MMRM) model without replacing missing values, assuming that all missing values are missing at random as well as an analysis using last observation carried forward (LOCF). Details will be described in the SAP.

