#### **14.3.1.5. Primary Estimand (Hypothetical assuming no concurrent procedures, irrespective of adherence to treatment)**

The primary estimand is defined as the following for the primary endpoint:

- Treatment difference in ICP measurement between Presendin and placebo at Week 24 for all patients who are randomised and start treatment, regardless of adherence to randomised treatment, where patients did not have medications or procedures likely to materially affect ICP.

The primary estimand for the initial secondary endpoint will be handled similarly to the primary endpoint using the “Hypothetical” approach. The initial secondary endpoint is defined as:

- Treatment difference in PMD between Presendin and placebo over 24-weeks for all patients who are randomised and start treatment, regardless of adherence to randomised treatment, where patients did not have medications or procedures likely to materially affect PMD.

Study Number: INVEX-CLIN-IIH-301 Protocol	Compound No.: Presendin
	Version: 5.0 for EU countries dated 08Dec2022

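### The secondary estimand assumes full adherence, but its analysis carries over placebo-arm imputation for adverse-event discontinuations, so estimator and estimand do not match

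*Protocol*

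**What the plan says.** The two ICP estimands differ in one clause. Section 14.3.1.5 (primary) takes the Week 24 difference "regardless of adherence to randomised treatment, where patients did not have medications or procedures likely to materially affect ICP". Section 14.3.1.6 (secondary) takes it "if all patients adhered to treatment, where patients did not have medications or procedures likely to materially affect ICP". The PMD estimands in the same two sections differ in the same way.

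Section 14.3.6 then sets the imputation rule by reason for missingness:

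- Missing at random, with withdrawal of consent as the example: "the missing data will be imputed using the treatment arm to which the patient was randomised to".
- Missing not at random: "e.g. early discontinuation due to adverse event), the missing data will be imputed to reflect outcomes in the placebo arm". For repeated measures the corresponding rule is a placebo-like course over time.
- Scope: "Our imputation strategy generally applies for data being set to missing by having an intercurrent event or data that is not captured at all".
- Secondary estimands: "For the analysis of the secondary estimands, the same model will be used, but additional treatment events will be considered which require further imputations".
- Left for later: "A detailed list of reasons for missingness and the corresponding way of imputation will be specified in the SAP". Section 14.3.1.6 also closes by deferring its details to the SAP.

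Elsewhere the protocol handles hypothetical events differently. In sections 14.3.1.1.1 to 14.3.1.1.3, ICP values removed because of ICP-lowering drugs, off-protocol lumbar punctures or surgical weight loss are replaced by imputations specific to the patient's own arm.

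**The concern.** Placebo-based imputation suits an estimand that counts patients whether or not they stayed on drug: someone who stops Presendin is given an outcome like that of someone not taking it. The secondary estimand asks something else. It needs the value a Presendin patient who stopped for an adverse event would have had on Presendin, and a placebo-arm value describes the very situation that this estimand assumes away.

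The only change that section 14.3.6 states for the secondary estimands is that more events lead to imputation. The reference arm for adverse-event discontinuations is left as it was. Followed as written, the plan would report under the label of an adherent effect a figure diluted by the adverse-event stoppers with missing data. The comparison with the primary estimand, which ought to show how much non-adherence costs, would be narrowed by the same amount.

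**Working it through.** **1. The passages side by side.** Take a Presendin patient who discontinues for an adverse event and has no Week 24 lumbar puncture.

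| Estimand | Value it calls for | Value section 14.3.6 supplies |
|---|---|---|
| Primary (14.3.1.5) | outcome whether or not on drug | placebo-like: coherent |
| Secondary (14.3.1.6) | outcome had the patient stayed on Presendin | placebo-like, by carry-over: does not match |

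For a placebo patient who stops for an adverse event the two rules coincide, so the mismatch sits in the Presendin arm only.

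**2. The plan's own ICP figure.** Section 14.2.1.1 gives a difference of 5 cm CSF, Week 24 SDs of 9.4 and 10.4, 60 final lumbar punctures per arm (72 in the second scenario), ANCOVA at the 5% level (taken as two-sided), and power of about 85% (91%). The correlation between baseline and Week 24 is not stated; 0.40 is assumed.

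- Pooled SD = √((9.4² + 10.4²)/2) = 9.91
- Residual SD = 9.91 × √(1 − 0.40²) = 9.08
- Standard error, 60 per arm = 9.08 × √(2/60) = 1.66
- Power = 85.4% at 60 per arm and 91.0% at 72 per arm

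The stated power reproduces. A correlation of 0.35 gives 83.9% and 89.8%, also close; a correlation of 0 gives 78.9% and 85.7%, which is not.

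**3. Size of the mismatch for ICP.** Let μ be the placebo mean and μ − 5 the Presendin mean under full adherence. Let f be the share of the Presendin arm imputed from placebo after an adverse-event stop, and assume that stoppers would have had the same mean effect as the rest had they adhered.

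- Expected difference = (1 − f)(μ − 5) + fμ − μ = −5(1 − f)
- f = 5%: 5 × 0.95 = 4.75 cm, a shift of 0.25 cm
- f = 10%: 5 × 0.90 = 4.50 cm, a shift of 0.50 cm

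Against the standard error of 1.66 cm, these shifts are 0.25/1.66 = 15% and 0.50/1.66 = 30% of one standard error.

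**4. Simulation check.** 120 per arm, correlation 0.40, true adherent effect 5 cm, adverse-event stoppers the only missing values, 10 imputations, 1,000 replicates, simulation error about 0.04 cm:

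| f (assumed) | Imputed from placebo | Imputed from own arm | Difference |
|---|---|---|---|
| 5% | 4.79 | 5.04 | 0.25 |
| 10% | 4.58 | 5.09 | 0.51 |

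A separate simulation with 60 of 120 Week 24 values missing per arm (8 imputations, 600 trials) gave 4.71 and 4.47 cm at the same two values of f, and 4.96 to 5.02 cm with own-arm imputation. Both agree with the formula.

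**5. PMD.** The direction is the same. The size also depends on when patients stop, because visits before the stop are kept and only later ones follow the placebo-like course. No PMD figure is computed here.

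**The case against.** **It is left to the SAP.** Both sections defer detail, and section 14.3.6 presents itself as a brief description. The SAP was not available for this check and may resolve the point. But the protocol does more than defer: it fixes the placebo rule for the adverse-event example and fixes the carry-over. A SAP that follows section 14.3.6 misses section 14.3.1.6; a SAP that imputes from the own arm departs from section 14.3.6.

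**The same model may mean only the regression.** The explanatory variables can be separated from the rule that assigns a reason to a reference arm, so this reading is possible. However, the carry-over sentence stands in the paragraph that describes how the models are applied by reason, and it states no exception. If the narrow reading is meant, the sentence still needs to say so, because the reference arm decides what is estimated.

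**Other analyses cover it.** The completer analysis, the missing-at-random MMRM for important secondary endpoints and the per-protocol population give related evidence. None targets the secondary estimand: completers can include patients who stopped drug and returned (section 12.2.1 encourages this), and the per-protocol set is a different population.

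**The effect is small and conservative.** This stands. The bias is towards no effect, concerns a secondary estimand, and at the assumed values of f is well under one standard error.

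A reader might also infer three stronger things that the protocol does not support:

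- *Observed off-drug Week 24 values are replaced by placebo-like ones.* This is not stated. The placebo example concerns missing data; for stoppers who still have a lumbar puncture, the protocol speaks only of further imputations and names no reference arm.
- *The contrast between the two estimands vanishes.* It shrinks but need not vanish: non-adherence classed as missing at random would still be imputed from the patient's own arm.
- *The share f is large because nausea and diarrhoea are very common.* Section 1.2.2.1 gives event frequencies for a different extended-release exenatide in type 2 diabetes, not stopping rates. Section 1.1.3 reports no withdrawals for adverse events in the phase 2 IIH trial, which was small (15 randomised), used the immediate-release product and ran 12 weeks. Neither source fixes f.

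**Conclusion.** The concern holds in a limited form. For Presendin patients whose data are missing after an adverse-event discontinuation, section 14.3.6 as written supplies an off-drug outcome to an estimand defined under full adherence, for ICP and for PMD. The ICP estimate is pulled towards no effect by the fraction f, so that 5 cm becomes 5(1 − f) cm. That is 0.25 to 0.5 cm for f of 5% to 10%, a range that is assumed because the protocol gives no rate. The formula rests on stoppers sharing the arm's mean effect had they adhered; the comparison with the standard error also rests on the assumed correlation of 0.40. For stoppers with an observed Week 24 value the protocol is silent on the reference arm, which is a gap to close and not a demonstrated bias. The primary estimand, the primary test and the stated power are not affected. The correction should be made because the reported adherent effect would otherwise not be the one defined.

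**What to change.** In section 14.3.6, replace the carry-over sentence with text to this effect: for the secondary estimands, values that are missing or set to missing because of treatment discontinuation or non-adherence, including for adverse events, are imputed from on-treatment data of the randomised arm; placebo-based imputation is kept for the primary estimand, or as a sensitivity analysis of the secondary one. This also settles the reference arm for stoppers with an observed Week 24 value. The alternative is to reword section 14.3.1.6 so that the estimand matches the imputation.

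The cost is one sentence in the protocol, a matching entry in the SAP and one further run of the multiple-imputation code. Trial conduct does not change. The downside is that the adherent estimate then rests on a missing-at-random assumption within arm for stoppers, which should be stated beside the result.
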